The process of THC dosing and administration will similar to those as described in Phase 2A. Participants will come to [name] for 5 study sessions. At the first visit, participants will undergo screening procedures to determine if they're eligible for the study. This will include a medical history interview, substance use history interview (timeline follow back), as well as a variety of questionnaires (to be completed by participants on study laptop; AUDIT, CUDIT, STAI, HADS, URGE, MEEQ, Who Assist). Participant vital signs, height, and weight will be measured, and participants will also provide a urine sample which will be tested for drugs and pregnancy (if applicable) to ensure participants are positive for THC. Participants are trained on the driving simulator computer tasks. If participants are determined to be eligible, they will be scheduled for the following two visits. A study physician will use the information from the medical history to determine the dronabinol dose. In addition to this, the physician/nurse will also collect a carbon monoxide (CO) measurement to biochemically establish smoking status. Dronabinol administration at visits 1-4 in the TCRC or CAM will be the same as described in phase 2A. On each study day, participants will undergo baseline fNIRS testing (see above "Cognitive Tasks during FNIRS testing"), substance use history interview (timeline follow back), baseline vital signs and weight measurement, a

driving simulator computer task refresher, and several questionnaires (PSQI, CWS). Dronabinol or placebo will be administered once morning procedures are complete, after which point heart rate, blood pressure, and responses to DEQ and BAES questionnaires will be monitored at 20 minute intervals. ETOH or placebo will be administered 60 minutes after dronabinol or placebo. The second fNIRS session will be conducted at approximately 100 minutes post dose, followed by driving simulator computer tasks. A field test of sobriety will be conducted following the second fNIRS assessment. The third fNIRS session will be conducted at approximately 280 minutes post dose, prior to participant discharge. See below for schematic:

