Ethanol dose and administration: We will obtain a breath alcohol concentration (BrAC) of approximately 0.05 BrAC (equal to 1-2 standard drinks). In order to obtain this precise BrAC, we will use established methods of dosing based on previously published procedures (e.g. King 2005, Alcohol Clin Exp Res, Vol 29, No 4, 2005: pp 547–552).

The required volume of 95% ethanol will be calculated from the nomogram published by Watson (1989), and diluted to a final concentration of 20% by volume with diet soda. The nomogram is based on total body water, estimated for each subject using standard equations based on gender, age, height, and weight (Watson et al., 1980). Doses will be prepared at the TCRC by a licensed nutritionist or at CAM by unblinded study staff. He/she will determine the dose according to our spreadsheet for dosing (attached).

In an attempt to standardize the drinking time to 8 minutes, the total dose will be split into 4 equal aliquots and placed in cups with lids. The subject will be given a cup every 2 minutes with instructions to sip the drink using a straw.

- Placebo Ethanol drink will be made as an equal volume of diet soda placed in identical cups with lids and straws. 0.25 ml of 95% ethanol should be floated on the top of the soda in each cup in an attempt to blind the participant.

The alcohol administration procedure will take place approximately 45 min before the start of the second fNIRS session. Before being administered alcohol, study staff will measure breath alcohol levels. Additionally, a study physician/nurse will assess subjects at each study visit prior to any study drug administration for signs of intoxication. Subjects will be terminated from the study if BrAC > 0 or if they exhibit clinical signs of intoxication at time of arrival for study visit.

During this phase, breathalyzer measurements will be taken approximately every 20 minutes after the alcohol administration procedure, until BrACs have returned to <0.01. Participants will be required to stay in the laboratory until BrACs have returned to <0.01. A member of our study staff will then (1) arrange cab service that has an approved partnership with MGH, and (2) escort the participant to the cab at the end of the study visit. Alternatively, it would be acceptable for participants to arrange travel home with a family member or friend. If they choose to do this, a study staff member will ensure that someone is there to bring them home prior to departure.

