The dronabinol capsules will be taken approximately 60 minutes before the alcohol administration procedure will begin, so that peak effects of each drug will be concurrent.

Driving Simulation: During this phase, we will use a computer-programmed driving simulator to assess motor coordination of the participants. The simulation will be programmed in STISIM on the computer and will be administered by a trained research coordinator. Subjects will be trained on this task during the screening task during the screening visit and given a refresher training on the task before testing. The task is performed on a laptop with the use of the keyboard, a joystick, and a foot pedal. Participants perform tasks where they must center an object on the screen using the joystick, in addition to identifying numbers with the tap of the foot pedal.

Blood Draw: During this phase, we will collect blood samples to track THC levels throughout the study. All blood samples will be taken by a catheter inserted in a forearm vein by a licensed nurse. One mL of blood will be taken pre-dose and approximately every 20-40 minutes post-dose until 300 minutes post-dose: 0, 40, 80, 100, 130, 160, 190, 210, 260, 300, for a total of 10 mL. Collected blood samples will be processed by an outside company, Immunalysis Corporation, to test for plasma concentrations of delta-9 THC.

[figure not shown]
Participants: 200 healthy, weekly or greater MJ users, aged 21-55, will be enrolled. Participants must test positive for cannabis and have no serious unstable medical illness to participate in Phase 2B (See Participant Selection Section).

Subjects who participated in Phase 1 or 2A will be eligible for Phase 2B, but enrollment in Phase 1 or 2A is not a requirement for Phase 2B. Therefore, new subjects who have not completed Phase 1 or 2A will also be eligible for Phase 2B so long as they are over the age of 21. Subjects who enroll in more than one phase of the study will be (1) re-consented for each phase and (2) counted again toward enrollment targets (i.e., counted toward the enrollment target listed for each study phase).

Phase 3. Investigate at which doses of dronabinol an effect on neurocognitive task performance or an effect on PFC activity can be observed.

Procedures will be identical to those of Phase 1 except that subjects will be scheduled for 3 study sessions. In each study session, they will be given a low, medium, or high

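### Phase 2B (advisory, participant safety): the only sobriety criterion for discharge is BrAC below 0.01, which does not measure dronabinol, and the assurance about physical tasks conflicts with testing timed to peak effect

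*Protocol*

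**What the plan says.** **Leaving.** In Section X, Phase 2B, Ethanol dose and administration, the protocol says: "Participants will be required to stay in the laboratory until BrACs have returned to <0.01". Staff then "escort the participant to the cab at the end of the study visit", or confirm that a relative or friend has come to take the participant home. The placebo drink is soda in four cups, and "0.25 ml of 95% ethanol should be floated on the top of the soda in each cup".

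The Phase 2B schedule also governs when people go: "The third fNIRS session will be conducted at approximately 280 minutes post dose, prior to participant discharge". Under Blood Draw, samples are taken "approximately every 20-40 minutes post-dose until 300 minutes post-dose". During the visit, "heart rate, blood pressure, and responses to DEQ and BAES questionnaires will be monitored at 20 minute intervals", but no value of any of these is made a condition of discharge. A physician or nurse looks for signs of intoxication before dosing; no matching check is written for departure.

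The dronabinol risk section gives onset at 0.5–1 h, peak effect at 2–4 h and psychoactive effects lasting 4–6 h. Study Drug and Dosing allows up to 80 mg in Phase 2B.

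**Physical tasks.** The ethanol risk section lists as a safeguard that nothing physical will be asked of intoxicated participants. The Phase 2B procedures say: "A field test of sobriety will be conducted following the second fNIRS assessment". The simulator, described as a measure of motor coordination using joystick and foot pedal, also follows that scan. Dronabinol is given about an hour before the drink "so that peak effects of each drug will be concurrent".

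**The concern.** A discharge rule should respond to the drugs given. Here two are given, one of them for its intoxicating effect, and the written sobriety threshold responds only to the other. On a THC + placebo-ethanol visit, a participant can satisfy the threshold all day and finish the last scheduled procedure while still inside the protocol's own window of psychoactive effect.

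The second issue is a listed safeguard that the procedures do not appear to follow. Testing people while they are affected is the purpose of the visit, so staff reading the risk section and staff following the schedule would be working to different statements. The dronabinol section names orthostatic hypotension and syncope on abrupt standing as occasional effects, and no standing check before the field test is stated.

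What is at stake is participant safety and the accuracy of the risk description.

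**Working it through.** The plan gives no figure of its own to reproduce. The check compares its stated times and doses.

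**1. Can the BrAC rule bind on a THC + placebo-ethanol visit?**
- Input from the protocol: four cups, each with 0.25 ml of 95% ethanol.
- Assumptions: ethanol density 0.789 g/ml, blood water fraction 0.8, body water 25–50 L, and BrAC read as equivalent to g/dL in blood.
- Ethanol: 4 × 0.25 × 0.95 × 0.789 = 0.75 g.
- Highest concentration = grams × 0.8 / litres / 10. At 25 L: 0.75 × 0.8 / 25 / 10 = 0.0024 g/dL. At 50 L: 0.0012 g/dL.
- Both are below 0.01, so the rule holds nobody on this visit. It is one of four visits and half of each participant's dronabinol visits.

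**2. Does the schedule fill the gap?**
- Effect window counted from dosing: 4 × 60 = 240 min to 6 × 60 = 360 min.
- Third scan: 360 − 280 = 80 min before the window's end. Last blood sample: 360 − 300 = 60 min before it.
- Counted from onset instead: 0.5 + 4 = 4.5 h (270 min) to 1 + 6 = 7 h (420 min), leaving up to 420 − 300 = 120 min. The protocol does not say which reading applies.

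**3. Does the rule help on THC + ethanol visits?**
- Protocol inputs: drink at 60 min, target BrAC 0.05.
- Assumptions: peak 30–60 min after drinking starts, elimination 0.010–0.020 g/dL per hour.
- Minutes after dronabinol to reach 0.01 = 60 + time to peak + 60 × (0.05 − 0.01) / rate.
- Fast: 60 + 30 + 120 = 210. Central (45 min to peak, 0.015): 60 + 45 + 160 = 265. Slow: 60 + 60 + 240 = 360.
- At 0.015 or faster, the rule is met before the 300-min sample. It reaches 360 min only at the slowest combination.

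**4. The assurance against the schedule.**
- The second scan starts at about 100 min. The SAP gives scan lengths of 360 s and 376 s, 736 s or 12.3 min together, so the field test comes at about 112 min at the earliest. With a 60-min session, as in Phase 1, it comes at about 160 min.
- Stated dronabinol peak: 120–240 min.
- Time since the drink started: 112 − 60 = 52 min to 160 − 60 = 100 min.
- Testing therefore falls close to or inside the peak window, in line with the stated intention that the two peaks coincide.

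**The case against.** The strongest reply is that BrAC is one of several controls and that the risk is already managed:

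- Travel home is by escorted cab or with a confirmed companion, and the schedule itself keeps people for about five hours after dosing.
- Licensed nurses monitor every visit, with vital signs and drug-effect ratings every 20 min, and a physician or nurse is on site or reachable by pager.
- Participant Selection excludes cardiovascular disease and unexplained syncope, and requires past alcohol and THC co-use without serious adverse effects.
- Participants are regular users who are expected to be tolerant, and a physician sets the dose.
- The Phase 1 text expects effects to have gone by 210–270 min.
- Visits are planned at about 7 hours.

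Most of this stands, and it is why the point is advisory. A reader might infer that BrAC is the only rule of any kind for leaving; that is wrong, since travel and the schedule also govern it. A reader might also infer from the 80 mg ceiling, against 50 mg in Phase 1, that effects last longer in Phase 2B. The documents do not support that, because the highest dose is generally for heavy daily users.

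What remains is that none of these is a check for residual dronabinol effect at departure. Phase 1 itself allows a repeat scan at 330 min if intoxication continues (for measurement rather than safety), which concedes that effects can persist. The 7 hours is a planned length, not a minimum stay: 420 min would reach 360 min post dose only if all pre-dose work took 60 min or less, and its duration is not stated.

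On the second issue, the assurance sits in the ethanol section and the field test's items are not described, so its physical nature is inferred. The simulator gives separate support, because the protocol itself calls it a test of motor coordination.

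**Conclusion.** The point holds as an advisory on Phase 2B participant safety. The only sobriety criterion for discharge in the available text does not measure dronabinol and never binds on one visit in four. At the last scheduled procedure, up to about 60 min of psychoactive effect may remain counting from dosing, or up to 120 min counting from onset. The assurance about physical tasks does not fit the scheduled testing and needs rewording.

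This rests on the assumptions shown above and on the text available. The Phase 2B schematic and the consent pages were not available, so a criterion stated there cannot be excluded.

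Three stronger readings are not supported. The documents do not show that participants were sent home intoxicated or harmed: they give no rate of residual effect or toxicity. They do not show that fainting is most likely at the time of the field test, because the syncope warning carries no timing. And the primary analysis is not threatened, since it uses the pre-dose scan and the scan at about 100 min, both well before discharge.

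**What to change.** If dosing continues:

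- **Discharge, at all four Phase 2B visits so that the blind holds.** Require BrAC below 0.01 and nurse or physician sign-off that the participant shows no clinical signs of intoxication. Base the sign-off on the heart rate, blood pressure and DEQ already collected, compared with that day's pre-dose values. Baseline vital signs are already listed for Phase 2B, but a pre-dose DEQ is not, so add one. Anyone not signed off stays until they are, with physician review at 360 min rather than automatic release, because the onset-based reading runs past 360 min.
- **Assurance.** Replace the sentence in the ethanol risk section with a statement that the field sobriety test and simulator are done after dosing, when participants may be intoxicated, with staff beside them.
- **Optional.** Take one standing blood pressure before the field test, with the limit set by the study physician.

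The cost is a short amendment, one extra DEQ per visit and, if adopted, one extra blood pressure. Some participants, at any of the four visits, would stay up to about 1 h longer, or more if effects persist. Any hold comes after all scans, so no primary outcome data are lost.

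The SAP's Sample Size Determination refers to scan collection in the past tense. If collection is complete, report the last DEQ rating and its time post dose by condition, and any syncope or falls during field tests.

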Phase 1: Participants will come to the MGH Martinos Center the morning of their study day. They will meet with a study doctor, sign the consent form, and complete screening for eligibility. Screening consists of a substance use history interview (timeline follow back), medical history interview, and a urine drug and pregnancy test. Those who are eligible will then complete baseline questionnaires, including the DEQ and BAES. Participants will be trained to become familiarized with fNIRS tasks and undergo the first fNIRS testing session. They will then be given a dose of dronabinol. Every 20 minutes,

they will complete the DEQ and BAES. fNIRS testing will be repeated at 100 min (thus the second fNIRS session will occur over 60 minutes comprising the timespan of 90-150 minutes after ingesting dronabinol, which is the median peak of pharmacokinetic effects). Participants will then have a one-hour break and undergo an optional third fNIRS testing session at 210-270 min (3.5-4.5 hrs after ingesting dronabinol, when expected effects have dissipated and the person is no longer clinically intoxicated) if time allows. Although not expected, if repeat fNIRS results at 210 min are consistent with continued intoxication, in order to obtain measurements following clinical intoxication, we may repeat the fNIRS testing at 330 minutes, 1.5 hours outside the peak window of intoxication).

The fNIRS device will only be operated by individuals who have received laser use training: [name], [name], [name], [name], [name], and [name].

[figure not shown]
In between testing sessions, participants will be allowed to read, use a laptop, or watch movies. They will be provided with snacks and drinks.

Phase 0 is expected to take approximately 2 months to complete. Phase 1 is expected to take approximately 1 year to complete. Phase 2 will begin after Phase 1 data collection is completed, and is expected to take approximately 1 year. Phase 3 data collection will start after completion of Phase 2, and is also expected to take approximately 1 year.

Phase 2A. Investigate the effect of THC on fNIRS brain signature and its association with self-reported intoxication, laboratory measures of impairment, and the gold-standard behavioral field test of driving impairment used by law enforcement, the primary classifier.

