dose of dronabinol (20 mg, 35 mg, 50 mg). In this single-blinded phase, the subject will not know which dose he/she is receiving. The protocol for the study visit will be identical. As there are three levels of drug exposures, there are 6 possible orders in which subjects can receive the three doses (e.g. high, medium, low; medium, low, high; etc). Subjects will be randomly assigned to one of the 6 possible orders according to a randomization schedule generated by the study staff using a random number generator and computer program. In order for a complete washout of effects, and to minimize the effect of repeat testing for the neuropsychology tasks, study visits must be at least 1 week apart. See below for schematic:

Subjects who participated in Phase 1 or 2 will be eligible for Phase 3, but enrollment in Phase 1 or 2 is not a requirement for Phase 3. Therefore, new subjects who have not completed Phase 1 or 2 will also be eligible for Phase 3.

Driving Simulation: During this phase, we will use a computer-programmed driving simulator to assess motor coordination of the participants. The simulation will be programmed in STISIM on the computer and will be administered by a trained research coordinator. Subjects will be trained on this task during the screening task during the screening visit and given a refresher training on the task before testing. The task is performed on a laptop with the use of the keyboard, a joystick, and a foot pedal. Participants perform tasks where they must center an object on the screen using the joystick, in addition to identifying numbers with the tap of the foot pedal.

Participants: 60 healthy, weekly or greater MJ users, aged 18-55, will be enrolled. Participants must test positive for cannabis, and negative for other addictive drugs and have no serious unstable medical illness to participate in the Phase III (See Participant Selection Section).

Biostatistical Analysis

Data variables collected for study

Standardized questionnaires, assessing drug use, personality characteristics, and anxiety will be collected, as well as task data and neural signaling data from the fNIRS testing sessions.

All data will be collected and managed using REDCap electronic data capture tools (Harris 2009) hosted with Partners HealthCare.

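### Phase 3 has no placebo session, so only differences between the three doses are randomised; the effect at any single dose, which Aim 2 asks for, rests on uncontrolled pre/post change

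*Protocol*

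**What the plan says.** Protocol section II (Aim 2) and the opening of Phase 3 in section X set the same objective: "Investigate at which doses of dronabinol an effect on neurocognitive task performance or an effect on PFC activity can be observed".

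The Phase 3 text then fixes the design. On sessions: "Procedures will be identical to those of Phase 1 except that subjects will be scheduled for 3 study sessions". The doses are 20, 35 and 50 mg, one per session. On randomisation: "As there are three levels of drug exposures, there are 6 possible orders in which subjects can receive the three doses". On blinding: "In this single-blinded phase, the subject will not know which dose he/she is receiving". Planned enrolment is 60. No placebo or zero-dose session is described.

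The Phase 1 procedures that Phase 3 takes over include task training before the first scan, a pre-dose fNIRS scan, a repeat scan at 100 minutes, and, time permitting, a later one: participants "undergo an optional third fNIRS testing session at 210-270 min". The protocol recognises practice effects and deals with them by spacing the visits: "to minimize the effect of repeat testing for the neuropsychology tasks, study visits must be at least 1 week apart".

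The SAP covers Phases 2A and 2B only. The protocol's own statistical methods paragraph names software and nothing more.

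**The concern.** Asking at which doses an effect can be seen is asking about each dose against no drug. Phase 3 has no session that measures what happens between the two scans when no drug is given. The blind conceals the dose level, not the fact that every session is active, so expectancy is present at all three visits. The one-week gap acts between visits and does nothing about two scans on the same day.

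Two errors become possible. A shift due only to time or repeat testing could be read as a drug effect at one dose or at all of them. Conversely, a real effect of equal size at all three doses would leave the between-dose comparisons null, and the design could not tell it from no effect.

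**Working it through.** **1. The plan's own figure.** Three doses give 3! = 6 orders, as the protocol states; 60 participants split evenly would be 60/6 = 10 per order. The count leaves no room for a placebo session: with a fourth treatment there would be 4! = 24 orders.

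**2. What the design can estimate.** Write τ for the non-drug change between the pre-dose and post-dose scans and δ(d) for the drug effect at dose d. The expected change in a session is Δ(d) = τ + δ(d).

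- Phase 3 observes Δ(20), Δ(35) and Δ(50): three quantities for four unknowns (τ and three δ).
- Differences cancel τ. For example, Δ(35) − Δ(20) = δ(35) − δ(20). These are estimable and protected by the random order.
- No single δ(d) can be recovered unless τ is known or assumed to be zero.
- A placebo session would add Δ(0) = τ and identify all three.

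The SAP's own coding for Phase 2 shows the same thing. It uses a pre/post scan term (Covariates) beside drug terms that are 0 before dosing (Statistical Model, Table 1). With an intercept, a post-dose term and one indicator per Phase 3 dose, the post-dose column equals the sum of the three dose columns.

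| Design | Rank / columns | With visit terms | Each dose vs placebo | Dose vs dose |
|---|---|---|---|---|
| 20, 35, 50 mg | 4 / 5 | 6 / 7 | not estimable | estimable |
| placebo, 20, 35, 50 mg | 5 / 5 | 8 / 8 | estimable | estimable |

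This result needs no assumption about effect sizes.

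**3. How much it could matter.** The documents give no drift, SD, correlation or Phase 3 test, so all of these are assumed: n = 60, no drug effect, and a paired t-test of post minus pre at each dose, two-sided 0.05. The SD of the change is SD × √(2(1 − r)). At r = 0.5 it equals the SD of a single score, so a drift of k SD has noncentrality k√60 on 59 degrees of freedom (critical value 2.00).

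| Drift (SD) | Noncentrality | P(a given dose is flagged) |
|---|---|---|
| 0 | 0 | 5% |
| 0.1 | 0.77 | 12% |
| 0.2 | 1.55 | 33% |
| 0.3 | 2.32 | 63% |

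For a drift of 0.2 SD, moving r from 0.3 to 0.7 moves the 33% to between 25% and 50%.

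**4. At least one of three doses flagged.** This depends on how a person's change scores correlate across sessions. With independence, 1 − (1 − 0.332)³ = 70% at 0.2 SD and 1 − (1 − 0.628)³ = 95% at 0.3 SD. By simulation, a correlation of 0.8 lowers these to about 48% and 77%. The ranges are therefore 48–70% and 77–95%.

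**The case against.** **Phase 3 is not blind to the effect of a single dose.** A reader might infer that it can only compare the doses with one another. That goes too far. Every session has a drug-free scan first, so change from baseline is measured at each dose; it is uncontrolled, not absent. A clear difference between doses would also show that at least one dose is active, though not which is the lowest active one.

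**Placebo data will exist.** It is tempting to say that nothing in the programme can help Aim 2. The documents do not support that either. Phase 3 starts after Phase 2 is complete, and people from Phases 1 and 2 may enrol, so drift under placebo will have been measured, for some participants possibly their own. What stands is that neither document plans to use it. The active-dose data in Phases 2A and 2B are no substitute, because the physician sets the dose mainly from expected tolerance, so dose and type of user are confounded.

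**No false claim is written into the plan.** A reader might also infer that following the plan would produce false findings at the rates above. No Phase 3 analysis is specified, so those rates describe what a per-dose pre/post test would do, not what is planned.

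**Mitigations.** Task training before the first scan should reduce early practice effects, but not fatigue, time of day or expectancy. The late scan is optional. At 3.5 to 4.5 hours it also begins before the shortest psychoactive duration given under Risks and Discomforts (4 to 6 hours) has passed, which sits badly with the Phase 1 description of that scan as taken after effects have worn off.

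**Weight.** The protocol calls the studies pilot work, and no SAP primary outcome addresses Aim 2. That limits the consequences but does not make the aim answerable.

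**Conclusion.** The point holds in this form: Phase 3 supports randomised comparisons between 20, 35 and 50 mg, while the effect at any one dose rests on a pre/post change in which drug and non-drug influences cannot be separated. The estimability result follows from the design alone. The false-flag rates (5% to 63% for a given dose; 48–70% or 77–95% for at least one dose at a drift of 0.2 or 0.3 SD) are illustrations. They rest on an assumed drift, a pre/post correlation of 0.5, 60 completers, and a per-dose test that the documents do not specify. With no drift the rate for a given dose is the nominal 5%. The mismatch between Aim 2 and the only phase designed for it should be corrected, because it changes what Phase 3 may conclude. Nothing here bears on the choice of dose levels.

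**What to change.** 1. Reword Aim 2 and the Phase 3 objective as within-person differences in pre-to-post change between the 20, 35 and 50 mg sessions.
2. State that a pre/post change at one dose will not by itself be called an effect of that dose.
3. Add a supportive comparison of each dose's change with the change on the Phase 2A placebo visit (second scan at about 90 minutes) and on the Phase 2B double-placebo visit (about 100 minutes). Label it external and non-randomised. List the mismatches: scan time in 2A, the placebo drink in 2B, and expectancy, since Phase 2 participants may receive placebo whereas Phase 3 participants always receive drug.

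The cost is a change of wording and one added analysis of data that Phase 2 will already have collected. The downside is a weaker claim for Phase 3.
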